## 1. BACKGROUND AND RATIONALE

A substantial contributor to social inequalities in health is diet [1], [2]. The dietary quality of people of lower socioeconomic status (SES) is poorer than that of people of higher SES [3], [4] and particularly rich in energy [5], [6] which likely contributes to the development of obesity and of a larger disease burden among people of lower SES [7].

Eating out of home has been associated to higher energy intake, weight gain and obesity [8], [9]. Yet, the popularity and availability of ready-to-eat meals have risen considerably over the last few decades [10], [11]. In this context, there is an increasing interest in interventions that aim at reducing the energy intake from food prepared out-of-home [12]–[14].

Information-based nutrition interventions (e.g., energy labelling on food menus) are one of the most common approaches to influence food choices [15], [16]. However, information-based interventions have been suggested to be less effective among people of lower compared to higher SES [17], [18] and therefore they may inadvertently widen inequalities in diet. Structural interventions that target core features of the food environment (e.g., increasing the availability of lower energy foods) are an alternative intervention approach do not depend on a sustained ‘agentic’ individual response [15], [19].

Information-based interventions typically rely on people understanding health consequences of what they eat and being motivated by health in their food choices [19]. Yet, health may be a less influential motive for food choice among people of lower SES [20]. Thus, SES based differences in food choice motives and health literacy may explain why information-based interventions would be less effective among people of lower vs. higher SES.

Moreover, the overall effect of energy labelling is small or unclear, as depicted in recent systematic reviews [21]–[23]. A possibility that has not been tested to date is that the effect of kcal labelling on purchasing behaviour is dependent on peoples’ existing knowledge about the energy content of menu items, whereby energy labelling is most effective when people are making food choices from unfamiliar menus and therefore are less able to distinguish from the lower and high energy menu items.

## 2. OBJECTIVES, OUTCOMES MEASURES AND HYPOTHESES

OBJECTIVES	OUTCOME MEASURES	HYPOTHESES
Primary objective  To examine the effect that an information-based intervention (energy labelling)	Energy (kcal) of the ordered meal.	An increased availability of lower energy menu options will result in a decrease in total

and a structural intervention (increased availability of lower kcals options) have on kcals ordered in a hypothetical meal ordering task among participants of lower and higher SES.
		
energy ordered among both participants of lower and higher SES. However, energy labelling may exert a stronger effect on energy ordered among participants of higher vs. lower SES.

Secondary objectives
 
To examine the reasons why the effects that energy labelling have on kcals ordered may vary based on a participants' SES.
 
To examine the effect of labelling on familiar and unfamiliar cuisines menus.
	
Health motivation in food choices (questionnaire score).
 
Energy (kcal) of the ordered meals for familiar and unfamiliar cuisines.
	
The participants of higher SES will be more motivated by health in their food choices than participants of lower SES, which will mediate the relationship between SES and the effect of energy labelling on the total energy ordered.
 
Energy labelling will have a greater effect for unfamiliar compared to familiar cuisines.

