## 5. METHODS

### 5.1. Meal choice task

#### Procedure

Participants will be asked to select the meal options they would be most likely to choose from six different dining out scenarios. Participants will be randomly allocated to one of the following group:

- baseline availability & no energy labelling (C: *control*);
- baseline availability & energy labelling (CL: *kcal labelling*);
- increased availability of lower energy options & no energy labelling (A: *availability*);
- increased availability of lower energy options & energy labelling (AL: *availability and kcal labelling*).

For each dining out scenario participants will be asked to imagine that they are eating out with friends for dinner at a [...] style restaurant. They will first be shown an image of the restaurant from the outside, before being shown an image of the inside of the restaurant and then the menu.

Participants will be asked to make their main dish selection from a menu including 10 main dishes options.

In order to examine whether participants are more likely to order 'additional' food as a result of ordering a lower energy option, after selecting their main dish option participants will be shown a 'sides' section of the menu displaying 5 sides dependent on dining out scenario. Participants will be asked whether they would order an additional side with their meal and if they select 'yes', they will select their side. The same options will be shown in all conditions, although in the no energy labelling conditions (C and A) there will be no kcal information next to menu options and in the energy labelling conditions (CL and AL) there will be kcal information next to each menu options. On the next page, this will be repeated for the dessert menu. The dessert menu will display 5 dessert options dependent on dining out scenario. As described for the 'sides' section, the same dessert options will be shown in all conditions and kcal information will be displayed in the energy labelling conditions (CL and AL).

The six dining out scenarios will be randomised in order. Additionally, the order of the dishes in each main menu was counterbalanced as explained in **Appendix A**. For the sides and desserts menus, two variants with different random order of the items will be created for each condition.

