### 7.2. Variables description

#### Primary outcome

The main outcome variable is the **energy of the main** selected in each dining out scenario in kcal.

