#### Secondary outcome

##### **From the meal choice task:**

We will also calculate the **total energy** of the selected meal. It will be calculated by summing the kcal of the selected main, side and dessert.

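### Section 2 states its outcome and hypotheses on the energy of the whole meal, but Section 7 analyses only the main dish and specifies no analysis of total energy

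*Combined protocol and SAP*

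**What the plan says.** Section 2 sets the outcome for the primary objective as "Energy (kcal) of the ordered meal". The availability hypothesis predicts a fall in total "energy ordered among both participants of lower and higher SES". The mediation hypothesis is that higher-SES participants are more motivated by health, "which will mediate the relationship between SES and the effect of energy labelling on the total energy ordered". The familiarity outcome is "Energy (kcal) of the ordered meals for familiar and unfamiliar cuisines". Section 2 never mentions the main dish.

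Section 7.2, under its primary outcome heading, says: "The main outcome variable is the energy of the main selected in each dining out scenario in kcal". Total energy appears there as a secondary outcome: "It will be calculated by summing the kcal of the selected main, side and dessert". Section 7.5 sets the alpha for secondary analyses at 0.01. Appendix K tells participants that total energy will be compared across the four conditions.

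Section 5.1 gives the reason for the sides step: "In order to examine whether participants are more likely to order" additional food after picking a lower energy option. The step records a yes/no answer: "Participants will be asked whether they would order an additional side with their meal and if they select" yes, they then pick one. The dessert step repeats this. Side and dessert options are the same in all conditions, with kcal shown in the labelling conditions. The availability intervention replaces four of the ten mains and nothing else.

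**The concern.** The two sections name different variables. A meal is a main plus an optional side and an optional dessert, and Section 7.2 itself separates the main from the sum.

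The difference matters because the two interventions act on different parts of the meal. Availability changes only the mains. If people who are offered lighter mains add a side or dessert more often, main energy falls by more than total energy does. Section 5.1 shows that the authors had this possibility in mind. Labelling covers all three courses, so a main-only outcome leaves out whatever labels do to sides and desserts. A report that followed Section 7 exactly would have no planned result on which to accept or reject the Section 2 hypotheses about total energy.

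**Working it through.** The plan gives no figure on this point, so the check is mainly a reading of each energy analysis for its dependent variable.

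| Analysis | Where | Dependent variable |
|---|---|---|
| Overall mixed model | 7.4 | Energy of the main |
| Models stratified by familiarity | 7.4 | Energy of the main |
| Models stratified by education | 7.4 | Energy of the main |
| Sensitivity analyses (repeats of the main analyses) | 7.4 | Energy of the main |
| Moderated mediation | 7.5 | Participant average energy of the mains |
| Debriefing models | 7.5 | Questionnaire items, not energy |
| Power statement | 7.6 | Energy of the main |

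Leaving aside the sensitivity repeats, total energy is the outcome in 0 of 4 energy analyses. The side and dessert yes/no answers are used in none.

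**Why the main cannot stand in for the total.** Count an unordered side or dessert as 0 kcal. For any contrast between conditions, the mean differences add up:

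D(total) = D(main) + D(side) + D(dessert)

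The planned models estimate D(main) only. That equals D(total) only if the other two terms sum to zero. Neither term is estimated, and the documents give no side or dessert energies from which to bound them.

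**Illustration of scale only.** The rise in the share of meals with an added item that would cancel a fall in main energy is the fall divided by the kcal per added item. The item energies of 200, 400 and 600 kcal are assumed.

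- *47 kcal fall* (the labelling effect cited in 7.6): 47/200 = 23.5, 47/400 = 11.8 and 47/600 = 7.8 percentage points.
- *American menu in Appendix A:* the ten baseline mains sum to 9,730 kcal, a mean of 973. The highest and lowest dishes stay, and four dishes above 600 kcal become dishes of at most 600. The smallest possible change is (650 + 790 + 870 + 970) − 4 × 600 = 880 kcal, so the menu mean falls by at least 88 kcal. If choices were spread evenly over the menu (assumed), break-even is 88/200 = 44, 88/400 = 22 and 88/600 = 15 points.

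**Precision for total energy.** Its SD is not given. Take the 7.6 variance of 47,244 at both levels, 6 meals and 500 v 500 participants. The SD of a participant mean is √(47,244 + 47,244/6) = 234.8 kcal, and the SE of a difference is 234.8 × √(2/500) = 14.85 kcal. If the SD for total energy were 1 to 2 times this (assumed), power for 47 kcal would be:

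- at alpha 0.05: Φ(3.165 − 1.960) = 0.89, down to Φ(1.583 − 1.960) = 0.35;
- at alpha 0.01: Φ(3.165 − 2.576) = 0.72, down to Φ(1.583 − 2.576) = 0.16.

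**Reach of a yes/no comparison.** With 500 v 500, 6 meals each, alpha 0.01 and 80% power, the detectable rise is (2.576 + 0.842) × √[p(1−p) × (1+5ρ)/6 × 4/1000]. For p = 0.3 and ρ = 0.2 this is 3.418 × 0.0167 = 5.7 points. For p = 0.5 and ρ = 0.5 it is 3.418 × 0.0242 = 8.3 points. Both p and ρ are assumed.

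**The case against.** The strongest reply is that the primary analysis is not in doubt. Section 7.2 names the main under a primary outcome heading, and every model and the power statement agree. Section 2 has a column of outcome measures beside a primary objective and does not use the term primary outcome. The documents also call the main dish the main meal (Section 6, Appendix H), so the Section 2 wording may simply be loose. Total energy is defined and has an alpha, and its data are collected. What is missing is about one sentence.

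Most of this stands. A reader might infer that the analyst is free to choose the primary outcome once results are known. Section 7 does not support that, because it leaves no choice of primary dependent variable. A reader might also infer that total energy was overlooked or that the design fails. That is not supported either: the variable is prespecified, and only its analysis is absent.

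The loose-wording defence does not go far enough. Section 2 also refers to total energy ordered, and Section 7.2 uses meal for the sum of the three courses. Defining a variable and announcing a comparison in Appendix K do not specify a model.

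A further tempting reading is that a very small rise in side or dessert ordering would wipe out the effect. Taking 2% of the 706 kcal in 7.6 gives 14 kcal, and break-even rises of only 7.1, 3.5 or 2.4 points at 200, 400 or 600 kcal per item. But 2% is the effect the plan says it can detect, not the one it expects, and 706 kcal comes from labelling trials. Section 7.6 expects about 7% for labelling and similar or larger effects for availability. Those small figures are not an expected availability result.

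**Conclusion.** The mismatch and the gap are both real. Section 2 states its outcome and its availability and mediation hypotheses on the whole meal, Section 7 tests the main dish, and no analysis is specified for total energy. Main-only models cannot show compensation, or labelling effects, on the other courses, so they cannot support the total-energy hypotheses. This conclusion rests on the text and on the additive identity, not on any assumed number.

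Neither the size nor the presence of compensation can be derived from the documents. The break-even figures are illustrations that depend on assumed item energies and, for the American menu, on evenly spread choices. Inference on the main dish is unaffected. The point should be fixed before data are seen, but it does not invalidate the trial.

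**What to change.** 1. **Align the outcome.** Keep energy of the main as primary, since all of Section 7 is built on it, and reword the Section 2 outcomes and hypotheses to match, including those for mediation and familiarity. List total energy there as a secondary outcome.
2. **Specify the total-energy analysis.** In Section 7.5, state that the Section 7.4 mixed model and its sensitivity analyses will be repeated with total energy as the dependent variable, counting an unordered side or dessert as 0 kcal, at alpha 0.01. Report estimates with confidence intervals.
3. **Limit the claims.** Base any statement about total energy ordered on that result only.
4. **Optional.** Report side and dessert ordering by randomised condition, for example with mixed logistic models with a participant random intercept. This estimates the effect of the condition. It does not estimate the effect of choosing a lower energy main, which is how Section 5.1 phrases the question.

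The cost is some wording and one further set of models on data already collected. The stated objective becomes narrower. Total-energy estimates may be less precise, so a non-significant result should not be read as proof of compensation or of no effect. The optional comparison could miss rises below roughly 6 to 8 points under the assumptions shown. Making total energy primary instead is the larger edit: the Section 7.4 dependent variable would change, and power would have to be restated for an outcome whose SD the plan does not give.

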### 3. EXPERIMENTAL DESIGN

Participants will be enrolled in an online survey and make hypothetical menu choices. Participants will be randomized into a mixed-design experiment with 2x2 between-subjects conditions with factors of kcal labelling (absent vs. present) and availability (baseline availability of main dishes with  $\leq 600$ kcals vs. higher availability of main dishes with  $\leq 600$ kcals) and 6 repeated measures (3 familiar and 3 unfamiliar menus).

### 4. PARTICIPANTS AND RECRUITMENT

#### 4.1. Recruitment

Participants will be recruited through an online recruitment panel (Prolific) in which participants are compensated proportionate to the time it takes to complete the online study ( $\approx \$6$ /hour reward participants). Participants' recruitment will be stratified by gender (50% male, 50% female), student status (8% yes and 92% no) [24] and highest achieved education level (10% less than high school, 30% high school completion, 30% some college or associate's degree, 20% bachelor's degree, 10% advanced degree) to be representative of US adults [25].

#### 4.2. Inclusion criteria

- US residents, age  $\geq 18$
- Fluent in English
- Have access to a computer and Internet

#### 4.3. Exclusion criteria

- Having any dietary restriction:
  - Vegetarian
  - Vegan
  - Gluten-free
  - Sugar-free
  - Diary/lactose-free
  - Food allergy (e.g. milk, eggs, nut, wheat, fish, etc.)

## 5. METHODS

### 5.1. Meal choice task

#### Procedure

Participants will be asked to select the meal options they would be most likely to choose from six different dining out scenarios. Participants will be randomly allocated to one of the following group:

- baseline availability & no energy labelling (C: *control*);
- baseline availability & energy labelling (CL: *kcal labelling*);
- increased availability of lower energy options & no energy labelling (A: *availability*);
- increased availability of lower energy options & energy labelling (AL: *availability and kcal labelling*).

For each dining out scenario participants will be asked to imagine that they are eating out with friends for dinner at a [...] style restaurant. They will first be shown an image of the restaurant from the outside, before being shown an image of the inside of the restaurant and then the menu.

Participants will be asked to make their main dish selection from a menu including 10 main dishes options.

In order to examine whether participants are more likely to order 'additional' food as a result of ordering a lower energy option, after selecting their main dish option participants will be shown a 'sides' section of the menu displaying 5 sides dependent on dining out scenario. Participants will be asked whether they would order an additional side with their meal and if they select 'yes', they will select their side. The same options will be shown in all conditions, although in the no energy labelling conditions (C and A) there will be no kcal information next to menu options and in the energy labelling conditions (CL and AL) there will be kcal information next to each menu options. On the next page, this will be repeated for the dessert menu. The dessert menu will display 5 dessert options dependent on dining out scenario. As described for the 'sides' section, the same dessert options will be shown in all conditions and kcal information will be displayed in the energy labelling conditions (CL and AL).

The six dining out scenarios will be randomised in order. Additionally, the order of the dishes in each main menu was counterbalanced as explained in **Appendix A**. For the sides and desserts menus, two variants with different random order of the items will be created for each condition.

#### Menus

The design of the restaurant menus will be based on menus from existing US restaurants. In a recent study, 1,184 American adults were asked which of 34 national cuisines they had tried and whether

they liked or disliked them [26]; results are summarised in **Appendix B**. Based on these results we selected three familiar (tried by at least 90% of US people: American, Mexican and Italian cuisines) and three unfamiliar cuisines (never tried by approximately 50% of US people: Lebanese, Peruvian, Moroccan cuisines) for American people. Using the online menus of US restaurants offering the selected cuisines, we will then create sample menus for the six distinct restaurant cuisines, each consisting of 10 main dishes and a selection of between 5 sides and 5 desserts (including actual food names, description and prices).

For familiar cuisines, the menu-model restaurants will be US popular chain restaurants (>800 outlets across the country); for unfamiliar cuisines, they will be US restaurants offering these specific types of cuisines that will be chosen by searching for restaurants in large US cities: New-York, Los Angeles, Chicago, Houston (using Yelp, Tripadvisor). All the food items (and their description) included in the experimental menus will be based on existing US restaurants. Because kcal labelling is only mandatory for restaurant chains in the US, we will use external sources to calculate the energy content per 100g of the menu options available for unfamiliar cuisines (e.g., online recipes, national food composition databases). All the six menus will offer a similar range of main options in terms of energy content (i.e., similar min, median and max).

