### Interventions

LE options are main dishes ≤600 kcal because meals ≤600 kcal comply with the dietary recommendation for US adults (i.e., on average 2,000 kcal per day) assuming an energy repartition pattern of three main meal occasions, each accounting for 20–35 % of daily energy intake, and 1–2 snacking occasions, each accounting for 5–10 % of daily energy intake [27].

In the baseline availability conditions (C and CL) 1/10 main dishes on the menus will be 600 kcal or less and 9/10 will exceed 600 kcal. In the increased availability of lower energy options conditions (A and AL), the proportion of main dishes ≤ 600 kcal will be increased to 5/10 by replacing four of the > 600 kcal main dishes from the baseline availability conditions with lower energy main dishes, whilst holding the price of replaced menu items the same. The menu items with the highest and the lowest energy content will remain the same in order to ensure the range of energy is consistent across conditions. The difference in the mean energy content of the menus items between C/CL and A/AL conditions will be approx. the same for familiar and unfamiliar menus.

In the energy labelling conditions (L and AL) energy in kcal will be added next to each menu option and reference information on energy requirements will be displayed. The energy labelling format will be in line with the mandatory menu labelling policy published by the US Food and Drug Administration [28], which requires restaurants to:

- Disclose calories for standard menu items listed on menus and menu boards:
  - Calorie labelling is placed on the menu adjacent to the name or the price of the menu item in a manner in close proximity and clearly associated with the menu item;
- Include on menus a succinct statement concerning suggested caloric intake and a statement that additional nutrition information is available upon request:
  - The succinct statement ‘2,000 calories a day is used for general nutrition advice, but calorie needs vary’ must appear on the bottom of menu boards and at the bottom of each page of multi-page menus;

- The statement of availability 'Additional nutrition information available upon request' must appear on the bottom of the first page of a menu that lists standard menu items and at the bottom of the menu board

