### 7.6. Sample size

The best available evidence of the effect of kcal labelling on kcal ordered at restaurants is the meta-analysis of Crockett et al. 2018. The authors analysed the effects of 3 RCTs testing energy labelling in restaurants [21]. They demonstrated a statistically significant reduction of 47 kcal in energy purchased when menus were labelled. The weighted average kcal ordered in the no label condition was 706 kcal. These results suggest that we could expect a 7% energy reduction in the labelling condition compare to the control condition. Previous studies examining the effect of an increased availability of lower-energy products on food selection tend to produce similar or larger effects than kcal labelling tends to [39], [40].-In a previous trial we ran at virtual fast food restaurants ([osf.io/ajcr6](https://osf.io/ajcr6)), we found a between-subject variance of 47,224 for kcal ordered ( $SD = 217.3$ ).

In a two-level mixed model, including 6 observations per participant at level 1 and estimating a level 1 and level 2 variance of 47,244 for energy of the main, a sample size of 1,000 participants with  $\alpha = 0.05$  allows to detect 2% energy reduction and above at power = 0.93 due to labelling and/or availability, an additional 2% energy reduction (or above) in participants of higher educational qualification at power = 0.81 due to an interaction between labelling and highest educational qualification and/or an interaction between availability and highest educational qualification, an additional 2% energy reduction (or above) for unfamiliar menus at power = 0.86 due to an interaction between labelling and familiarity and/or an interaction between availability and familiarity (MLPowSim) [41].

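### The rule for building the menus leaves the spread of main-dish kcal free to differ between familiar and unfamiliar cuisines, so an equal response to labels can appear as a labelling*familiarity effect

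*Combined protocol and SAP*

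**What the plan says.** Section 2 lists as a secondary hypothesis: "Energy labelling will have a greater effect for unfamiliar compared to familiar cuisines". Section 7.4 tests it with the labelling*familiarity term in a linear mixed model for energy of the main. Familiarity is fixed by cuisine, three cuisines per level (section 7.2). The model has a participant random effect and no cuisine or menu term.

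Three rules make the menus comparable:

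- Section 5.1, Menus: "All the six menus will offer a similar range of main options in terms of energy content (i.e., similar min, median and max".
- Section 5.1, Interventions: "In the baseline availability conditions (C and CL) 1/10 main dishes on the menus will be 600 kcal or less". The share rises to five in ten under increased availability (A and AL), and the highest- and lowest-energy dishes stay the same.
- Section 5.1, Interventions: the difference in mean energy "between C/CL and A/AL conditions will be approx. the same for familiar and unfamiliar menus".

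The two classes of menu come from different sources. For familiar cuisines, "the menu-model restaurants will be US popular chain restaurants (>800 outlets across the country". For unfamiliar cuisines the models are restaurants found by online search in four large cities, and the team works out the kcal from recipes and food composition databases.

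Section 7.6 claims power for "an additional 2% energy reduction (or above) for unfamiliar menus at power = 0.86".

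**The concern.** The outcome is in kcal, so the size of a label effect depends on how much kcal a change of choice can save. On a menu whose dishes cluster near the median, a switch saves little. On a menu with many dishes near both ends, the same tendency to switch saves more. Minimum, median, maximum and the count at or below 600 kcal leave eight of the ten dishes considerable room to move. The equal mean shift between availability levels helps availability*familiarity, but it does not fix spread.

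If unfamiliar menus turned out wider than familiar ones, the labelling*familiarity term could be significant with no role for familiarity. If they turned out narrower, a real effect could be hidden. Because cuisine is nested in familiarity and no menu term is fitted, the model cannot tell the two apart. The individual familiarity score is only described, and the planned manipulation check asks whether people know the cuisines, not whether the menus are otherwise alike. A significant familiarity interaction also triggers stratified models (section 7.4) and changes how choices are averaged for the mediation analysis (section 7.5).

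**Working it through.** **Inputs from the plan.** 1,000 analysed, equal allocation, three menus per class, variance 47,244 at each level, label effect 47 kcal, reference 706 kcal (section 7.6); American baseline menu (Appendix A).

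**Assumptions added.** Logit choice, equal appeal of dishes before labelling, the same sensitivity to kcal on every menu, two-sided 5% test.

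**Precision of the test.** The participant variance cancels in the unfamiliar-minus-familiar difference:

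SE = sqrt(4 x 47,244 x (1/3 + 1/3) / 1,000) = 11.2 kcal.

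The target is 2% x 706 = 14.1 kcal. The closed-form power is Phi(14.1/11.2 - 1.96) = 0.24, so the stated 0.86 is not reproduced. The kcal baseline given to the power software is not stated, and that mismatch is a separate matter. Only the SE is used below.

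**Spread left open by the rule.** The American baseline menu has minimum 370, median 1005 and maximum 1360. Two constructed menus share these values and also have one dish at or below 600 kcal:

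- narrow: 370, 880, 920, 950, 980, 1030, 1060, 1090, 1130, 1360
- wide: 370, 630, 660, 690, 970, 1040, 1280, 1310, 1340, 1360

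**Label effect on each.** Choice probabilities are proportional to exp(-b x kcal). Setting b = 0.00052 gives a 47-kcal fall on the American menu. To first order the fall is b x variance (0.00052 x 86,661 = 45). The same b is then applied to the other two menus.

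| Menu | Mean | SD | Variance | Fall (kcal) | Fall / SD | Fall / variance |
|---|---|---|---|---|---|---|
| Narrow | 977 | 240 | 57,441 | 32.2 | 0.135 | 0.00056 |
| American | 973 | 294 | 86,661 | 47.0 | 0.160 | 0.00054 |
| Wide | 965 | 340 | 115,545 | 61.2 | 0.180 | 0.00053 |

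Narrow and wide differ by 61.2 - 32.2 = 29 kcal with no familiarity effect. This shows the mechanism; it is not an expected size. Dividing by SD leaves a gap of 0.180/0.135 - 1, about a third. Dividing by variance nearly removes it.

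**Random variation within the rule.** With the inner dishes drawn at random under the same constraints and three menus averaged per class, the artefact has SD of about 4-5 kcal. Its total spread with sampling error is sqrt(11.2^2 + 4^2) = 11.9 to sqrt(11.2^2 + 5^2) = 12.3 kcal. The false-positive rate is 2 x Phi(-1.96 x 11.2/11.9) = 0.065 to 2 x Phi(-1.96 x 11.2/12.3) = 0.073, about 0.07.

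**Systematic difference between classes.** For an artefact D, the chance of p < 0.05 is Phi(D/11.2 - 1.96) + Phi(-D/11.2 - 1.96):

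- D = 12 kcal: about 0.19
- D = 25 kcal: about 0.61

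**Smaller label effect.** If labels lower energy by only 14 kcal, contrasting menus within the rule (SD from 228 to 371) give an artefact of about 4-14 kcal and a rejection rate of 0.06-0.23.

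**The case against.** The strongest reply is that the menus are already constrained on several features, not on three statistics alone. This is right: the share of mains at or below 600 kcal, the fixed end dishes and the mean shift all narrow the choice. None of them fixes spread, though, and the constructed menus above meet every constraint that applies to a baseline menu.

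A second reply is that the 29-kcal pair is extreme. This also stands. It would need all three menus of one class to be tightly clustered and all three of the other to be two-humped. Under random variation, 98% of menus had an SD of 248-329, which excludes both. The realistic random case is a modest rise in the error rate. A larger artefact needs a systematic difference in spread, which the different sourcing makes possible but which no section shows.

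A reader might also infer that unmatched prices are read as familiarity, since the menus are built "including actual food names, description and prices" and the availability swap is made "whilst holding the price of replaced menu items the same". The documents do not support this. A general price difference between cuisines is present with and without labels, so it enters the familiarity main effect and changes the interaction by 0 kcal. Only a different relation of price to kcal within menus could bias it, and no such difference is documented. The price hold for swapped dishes serves a contrast between arms, so leaving prices unmatched across cuisines is not an inconsistency.

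**Conclusion.** The concern holds in a limited form. Kcal spread is not equated between familiar and unfamiliar menus, and the model cannot separate a spread difference from a familiarity effect on labelling. The likely cost is small if spread varies only at random (false-positive rate about 0.07) and material if the two sources differ systematically (about 0.19 at 12 kcal, about 0.61 at 25 kcal).

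These figures rest on logit choice, equal dish appeal, one sensitivity for all menus and a 47-kcal effect taken from energy purchased in restaurant trials. They cover baseline menus, whereas the tested term pools both availability levels. Only the American baseline menu is given, so the actual spreads are unknown.

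A reader might infer that the main labelling result is compromised. It is not: the hypothesis at risk is a secondary one.

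**What to change.** In section 5.1, Menus, extend the matching rule so that the familiar and unfamiliar sets also have similar mean and SD of main-dish kcal, at both availability levels. Keeping the SDs within 5% holds the artefact to about 47 x (1.05^2 - 1) = 4.8 kcal. Report mean, SD and price for each menu and condition.

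As a check, add one rerun of the labelling*familiarity test with the label effect scaled by the kcal variance of the menu shown, for example by multiplying the labelling indicator by that menu's variance relative to the average. Scaling by SD would leave much of the artefact in place, as the table shows. Prices need only be reported: a common price list is not required for this interaction and would give up the restaurants' own prices.

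The cost is slightly less freedom in choosing dishes and one extra model. The sample size does not change.
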